#### **Subject Selection:**

Subjects who will require bilateral cataract surgery will be considered. Evaluations will occur in the clinic of the Principal Investigator (PI) [name] at the Wolfe Eye Clinic.

#### Inclusion Criteria:

- Visually significant cataract 2-3+ undergoing uncomplicated cataract surgery with similar cataract grade in both eyes
- Unremarkable ocular health but inclusive of early AMD

#### Exclusion Criteria:

- H/o ocular surgery including corneal refractive surgery
- Compromised zonular integrity or stability
- Uncontrolled diabetes and diabetic retinopathy
- Small pupils
- H/o systemic inflammatory disease/uveitis
- H/o chronic pain medications (including narcotics) and benzodiazepine usage
- Abnormal liver or renal function

#### **Study Cost/Reimbursement:**

- Participation in this study will be of no additional cost to patients. Insurance will partake in the payment of study evaluation and standard cataract surgery. The additional data monitoring needed will be provided at no cost to patients and incurred by the Sponsor.
- At the completion of the study patients who have completed the study in its entirety will be mailed a check for \$150.00.

#### **Planned Data Analysis:**

The following analysis will be performed using STATA software (v16.1, College Station, TX). All continuous variables will be summarized using mean, standard deviation and standard error. All binary measures will be summarized as proportions with standard deviation. The results of the test for normality on each continuous measure (the Shapiro-Wilk test) will determine whether the paired t-test or the Wilcoxon Sign Rank test will be used. McNemar's test will be used to compare proportions in binary outcome data, and the chi-squared test will be used to analyze the categorical outcome.

The analysis will follow a hierarchical approach using the following order of testing, only proceeding to the next test if the prior test achieves statistical significance at a level of 0.05.

Primary endpoint: comparing low vs. high IOP groups

1. Proportion of patients requiring rescue medication for breakthrough pain

Secondary Endpoints: comparing low vs. high IOP groups

1. Discomfort/pain score (VAS) - CONTINUOUS
  - a. Phacoemulsification
  - b. I/A
  - c. Visco removal

2. Surgeon Experience - CONTINUOUS
  - a. Patient cooperation
  - b. Surgeon experience
3. Cost analysis of intraoperative medications used - CONTINUOUS
4. Discomfort/pain score (VAS) on subjects with axial length of >24.5mm - CONTINUOUS
  - a. Phacoemulsification
  - b. I/A
  - c. Visco removal
5. Post op day 1 patient survey on experience (Iowa Satisfaction with Anesthesia Scale (ISAS) - CONTINUOUS
6. Proportion of patients following each procedure who would undergo the same procedure again - BINARY
7. Proportion of patients following each procedure who would recommend the procedure to family and friends - BINARY
8. Time Interval between Surgery Completion and Discharge from Facility - CONTINUOUS
9. Post op day 1 survey on patient preference - Which eye was more comfortable? (R/L/Neither) - CATEGORICAL
10. Which surgical experience did you enjoy more? (R/L/Neither) – CATEGORICAL
11. Proportion of patients who experience a significant (as defined by Crandall) physiologic response by a masked anesthesiologist - BINARY
  - a. Change in diastolic BP from baseline
  - b. Change in systolic BP from baseline
  - c. Change in pulse rate from baseline

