**Study treatment & Methods:**

- Sequential cataract surgery with similar cataract grade 2-3+ based on LOCS III grading bilaterally; 2nd eye to be completed within 2-3 weeks of first eye
- Randomize first eye to low vs high IOP, contralateral eye receives opposite IOP
- Patient education on VAS with standard script
- Standard pre-op drops: 2 drops of cyclopentolate 1%, tropicamide 1%, flurbiprofen sodium (Ocufen 0.03%), phenylephrine hydrochloride 2.5%, and 3 drops of marcaine 0.05%
- After draping, patients receive OcuCoat on cornea and 3 drops of lidocaine, 1mg of Versed (midazolam for anxiety with no analgesic effects)
- If patients experienced breakthrough pain during surgery, additional topical anesthetic, intracameral lidocaine, and/or opioid will be used per surgeon discretion and stage recorded
- Physiological responses recorded: Anesthesiologist will monitor patients per standard of care but will record additional BP/HR values at the start of the case (room entry), 4 minutes after versed is administered, during phacoemulsification, and during viscoelastic removal.
- Technique and Intraoperative recordings:
  - Single surgeon, uniform corneal incision construction (size, architecture) and use of Intrepid coaxial polymer I/A curved, Alcon OVD-Duovisc; Horizontal phaco-chop technique with preestablished, standardized, and optimized fluidic parameters
  - VAS score is asked at beginning of: phaco, cortex infusion /aspiration, viscoelastic removal
  - Surgeon assessment on patient cooperation and overall experience
  - Recording of intraoperative phacoemulsification metrics to ensure comparable parameters to eliminate variables other than IOP that may contribute to physiological changes
  - CDE, ASM activation, total aspiration time

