#### **Secondary endpoints:**

- Discomfort/pain score at phaco, I/A, visco removal
- Surgeon Experience: Assessment on cooperation & experience
- Cost-analysis on intraoperative medications utilized in high vs low IOP groups
- Breakthrough pain and discomfort/pain score on subjects with axial length of >24.5mm
- Post op day 1 patient survey on experience (Iowa Satisfaction with Anesthesia Scale (ISAS))
- Post op day 1 survey on patient preference - What eye was more comfortable? (R/L)
- What surgical experience did you enjoy more? (R/L)
- x% of eyes would undergo the same procedure again
- x% of eyes would recommend the procedure to family and friends
- Physiologic responses by masked anesthesiologist: BP, pulse rate
- Time Interval between Surgery Completion and Discharge from Facility

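### Blood pressure and pulse are tested only as a yes/no response, which costs precision in the one outcome with a stated masked assessor

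*Protocol*

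**What the plan says.** The Protocol's list of secondary endpoints names the outcome as "Physiologic responses by masked anesthesiologist: BP, pulse rate", with no dichotomy. Under Study treatment & Methods the anesthesiologist is to "record additional BP/HR values at the start of the case (room entry), 4 minutes after versed is administered, during phacoemulsification, and during viscoelastic removal". The design is paired: "Randomize first eye to low vs high IOP, contralateral eye receives opposite IOP".

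The Planned Data Analysis then fixes the tested form. Item 11 begins "Proportion of patients who experience a significant" and ends "physiologic response by a masked anesthesiologist - BINARY". Its three parts are changes from baseline in diastolic pressure, systolic pressure ("Change in systolic BP from baseline") and pulse rate. The section's general rule is that "McNemar's test will be used to compare proportions in binary outcome data", while continuous outcomes get a paired t-test or a Wilcoxon signed-rank test, chosen by a normality test. Item 11 therefore goes to McNemar. The definition of a significant change is taken from a source cited as number 11. The reference list ends at 8, and the text states no cut-off.

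**The concern.** The study already collects paired, continuous measurements and already has a paired continuous test in its plan, yet item 11 reduces each measure to whether a threshold was crossed. A change just short of the cut-off counts the same as no change, and one just past it the same as a very large one.

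The outcome matters more than its rank suggests. No other endpoint names a masked assessor. Rescue medication, the primary endpoint, is given at the surgeon's discretion, and cooperation and surgical experience are graded by the surgeon. Blood pressure and pulse are the natural place to look for objective support, and a low-powered test there makes a non-significant result hard to interpret.

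This is not a detail left to an SAP that is not shown: the protocol itself assigns the scale and, through its general rule, the test.

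**Working it through.** **1. The plan's own figures.** There is none for item 11: no response rate, cut-off, standard deviation or between-eye correlation. The only sizing is for the primary endpoint (15% versus 0%, two-sided 0.05, 80% power, 58 pairs). The McNemar normal formula gives 50 pairs, or about 57 after adding the continuity term 1/0.15 = 6.7, close to 58. The sizing says nothing about item 11, but it supplies the planned number of 85 pairs, the alpha and the power used below.

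**2. Assumptions supplied here.** The change from baseline is normal. A share p of patients respond, with p from 10% to 50%. The correlation between a patient's two operations is ρ, from 0 to 0.7.

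**3. Independent eyes.** The efficiency of the yes/no outcome relative to the continuous one is E = φ(c)² / [p(1 − p)], where c is the normal cut-point leaving p above it.

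- p = 50%: 0.1592 / 0.25 = 0.637, a loss of 36%
- p = 20%: 0.0784 / 0.16 = 0.490, a loss of 51%
- p = 10%: 0.0308 / 0.09 = 0.342, a loss of 66%

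**4. Paired eyes.** McNemar's variance depends on the discordant probability 2(p − p₁₁), where p₁₁ is the chance that both operations produce a response. The continuous difference has variance 2(1 − ρ). Hence E = φ(c)²(1 − ρ) / (p − p₁₁). For example, at ρ = 0.5 and p = 50%, p₁₁ = 1/4 + arcsin(0.5)/(2π) = 1/3, so E = 0.1592 × 0.5 / 0.1667 = 0.477, a loss of 52%.

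Information lost:

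| ρ | p = 50% | p = 30% | p = 20% | p = 10% |
|---|---|---|---|---|
| 0 | 36% | 42% | 51% | 66% |
| 0.3 | 45% | 51% | 59% | 72% |
| 0.5 | 52% | 58% | 65% | 77% |
| 0.7 | 62% | 67% | 73% | 83% |

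**5. In terms of power.** Take 85 pairs and the shift that the continuous paired test detects with 80% power: (1.960 + 0.842) × √[2(1 − ρ)/85] standard deviations, which is 0.304 at ρ = 0.5. McNemar's power for the same shift, as p goes from 50% down to 10%, is:

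- ρ = 0.3: 53% down to 30%
- ρ = 0.5: 47% down to 25%
- ρ = 0.7: 39% down to 20%

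With 72 pairs (85 × 0.85) the shift is larger, but these powers change by less than one percentage point.

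**6. Place in the hierarchy.** Before item 11 come the primary test (1), VAS at three stages (3), surgeon assessments (2), cost (1), VAS in long eyes (3), and items 5 to 10 (6). That makes 1 + 3 + 2 + 1 + 3 + 6 = 16 tests.

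**The case against.** The strongest reply is that it hardly matters. Item 11 is tested only if 16 earlier tests all reach 0.05. As an illustration, if these were independent with 80% power each, the chance of getting there is 0.8¹⁶, about 3%; with 90% power it is 0.9¹⁶, about 19%. Correlation would raise both. This stands, and it limits the formal consequence. It does not remove the gain in precision, since the estimate and its interval can be read whether or not the gate opens.

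A responder analysis with a published definition is also a legitimate choice, and the short label in the endpoint list is compatible with it. That stands too: there is no contradiction, only a less efficient choice of the tested form.

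Four stronger readings may tempt a reader, and the protocol does not support them:

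- That a third to two thirds of the information is definitely lost. This range depends on response rates that the protocol never gives and on treating the eyes as independent. It is not a ceiling either: with paired eyes, or a rarer response (78% lost at p = 5% even without correlation), the loss is larger.
- That the continuous values go unused. All continuous variables are to be summarised with means and standard deviations, so descriptive comparison is not excluded. They are only not tested.
- That the threshold has no traceable source. The text also names the source by its first author, and only reference 2, the comparison of topical anesthesia with and without intracameral lidocaine, has that first author. Number 11 looks like a numbering slip.
- That blood pressure and pulse are a clean check on the primary endpoint. Rescue may be given during the operation, and is assumed in 15% of high-IOP against 0% of low-IOP patients, so readings at viscoelastic removal may already reflect it.

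**Conclusion.** The point holds as a modest improvement. Item 11 puts a paired continuous measurement through a binary test. Under a normal model with 10% to 50% responders, this loses about 36% to 66% of the information if the eyes are independent, and about 45% to 83% with a between-eye correlation of 0.3 to 0.7. Response rate, correlation and normality are all assumptions. The figures cover the dichotomy alone, not any further loss from choosing among or collapsing the later readings.

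A null result would be weakly informative. A reader might go further and call it uninformative, but some power remains throughout the range examined. Because the endpoint is secondary and last in the order, the effect on the trial's formal conclusions is small.

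**What to change.** In item 11, make the tested quantity the within-patient low-minus-high difference in change from room entry to phaco, for systolic pressure, diastolic pressure and pulse. Use the paired continuous test already in the plan and report 95% confidence intervals. Three tests replace three, so the hierarchy keeps its length.

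Report the change to viscoelastic removal as supportive, noting that those readings may follow rescue medication. Keep the responder proportion as supportive too, with its cut-off stated in the text and the citation number corrected.

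The cost is wording only, as the data are already being collected. The one downside is that the responder figure comparable with the cited study is no longer the tested result.

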### **Data Collection and Management:**

Study worksheets will be created before data collection. At the conclusion of each week, all completed patients will have data collected transferred to a password protected excel spreadsheet. There will be no names placed into this document – only medical record numbers will be used for identification. To facilitate data entry, the worksheets coincide with excel. The design of the data entry screens will follow the same flow as the provided worksheets to ensure minimal issues during data entry. All worksheets collected for study (anesthesia and surgeon) will be placed into study binders. Study binders will be placed inside of locked cabinet.

Any corrections to the worksheets will be made by drawing a single line through the incorrect entry, recording the correct information, and initialing and dating the change. The study worksheets and data entered in the Excel files will be audited by the study sponsor.

Data is protected by preventing unauthorized users from accessing the system with the use of username and password combination. In addition, each individual user will be assigned a specific role in the Microsoft Excel which will grant that user the right to view, edit and/or delete the data.

All clinical data generated in the study will be submitted to the Sponsor or its designee for quality assurance review and statistical analysis. All worksheets and data entered in Excel files will be reviewed for completeness and evident recording errors will be rectified by contact with the appropriate clinical site.

#### **Study Administrations:**

Ethical and Regulatory Considerations- the study is conducted in accordance with the following:

- Protocol and study-related plans and documents
- Local regulations, as applicable
- Good Clinical Practices, as outlined in the ICH Harmonized Tripartite Guideline for GCP (ICH E6(R2))
- The ethical principles established by the Declaration of Helsinki
- Regional participant data protection laws and regulations

#### **Institutional Review Board (IRB):**

The study site must maintain an accurate and complete record of all reports, documents and other submissions made to the Institutional Review Board (IRB) concerning this protocol.

The investigator must supply ongoing study progress reports to the IRB, per local requirements, such as updates on SAEs, protocol deviations and amendments, ICF revisions, relevant sponsor communication, enrollment updates, etc. In addition, the investigator must notify the IRB at the closure of the study.

#### **Informed Consent:**

It is the responsibility of the investigator or his/her designee to inform each subject of the purpose of this study, including possible risks and benefits and document the informed consent process in the subject's chart. Prior to entry into the study or initiation of any study-related testing, the subject must read, sign and date the informed consent form. If the subject's vision is impaired to the point where they cannot read the informed consent document, the document will be read to the subject. The person executing the consent must also sign and date the consent form. One original informed consent form is to be retained by the study site, and a copy is to be given to the subject.

#### **Protocol Amendments:**

This protocol must be followed as written. Any change or addition to this protocol that impacts subject safety, or the validity of the study requires a written protocol amendment that must be approved in writing by the IRB and any required regulatory authorities before implementation.

#### **Record Keeping and Retention:**

Data generated for the study should be stored in a limited-access file area and be accessible only to representatives of the study site. All reports and communications relating to study participants will identify participants only by subject identification number. Complete subject identification will be kept by the investigator. This information will be treated with strict adherence to professional standards of confidentiality.

- Documents Provided to Sponsor: A copy of the IRB approved informed consent form.
- Documents that study site will retain:
  - All original informed consent forms with required signatures.
  - All participant source documents, etc.
  - All IRB correspondence (i.e., informed consent [including any approved revisions], protocol, AE, advertisements, newsletters).

- Copies of all pertinent correspondence pertaining to the study (except budget issues) between the Sponsor or its designee and the site

#### **Publication:**

Data and information generated in this study are the exclusive property of the Sponsor and are confidential. At the end of the study, a clinical study report will be written by the Sponsor or its designee. Written approval from the Sponsor is required before disclosing any information relative to this clinical study, and no publications initiated by investigators may be published until all protocol-defined results are published in a manuscript. Publication of the results must be based on appropriate analyses and review of the complete data. Authorship may be determined based on enrollment of eligible subjects or contribution to the design, conduct, or interpretation of the study. Investigators agree to have their names listed as an investigator in any publication reporting the results from this study, whether they are an author on the publication. The preparation and submittal for publication of manuscripts and presentations containing the study results shall be in accordance with a process determined by mutual written agreement between the Sponsor and participating institutions. The publication or presentation of any study results shall comply with all applicable privacy laws.

